## **7.0 STATISTICAL CONSIDERATIONS**

### **7.1 Study Design / Study Endpoints**

This is a prospective two arm randomized trial in which patients will complete the xerostomia questionnaire at six time points, including baseline and five post-radiation time points. The primary study endpoint is the change in composite xerostomia score (on a scale of 0-100, converted from the xerostomia questionnaire that is on a scale from 0-80; this conversion is made by adding up the values from questions 1-8 and dividing by 0.8, thus converting an 80 point scale into a 100 point scale) between baseline and 1 month. The xerostomia score change will be assessed using two methods: 1. Proportion of patients with a minimally clinically important difference and 2. Mean change. In LCCC 1540 (at n=41), the mean xerostomia score change from baseline to 1 month was 17.8, with a standard deviation of 26.0. The minimally clinically important difference is commonly defined as  $\frac{1}{2}$  of the standard deviation. For sample size calculations, we will therefore define a  $\geq 15$  point xerostomia score increase as a minimally clinically important difference.

### **7.2 Sample Size and Accrual**

In LCCC 1540 (at n=41), the proportion of patients experiencing a  $\geq 15$  point xerostomia score increase was 42% (95% CI 26-57%). Setting the null hypothesis proportion of patients experiencing  $\geq 15$  point xerostomia score increase at 42% and an alternative proportion of 14%, 31 patients in each group are needed for 80% power to detect this difference using a two group chi-square test with a one-sided significance of 0.05.

In order to have 62 patients with both baseline and one month post-treatment surveys, we will target our enrollment for this study at 90 patients, given the patterns of patient attrition observed in LCCC 1540 and early enrollment to this study (assuming 70% completion rate). To obtain this target accrual, we anticipate an accrual period of roughly 3-5 years. This number is based on extrapolated accrual rates from LCCC 1540, which accrued 100 patients over roughly 2 years and the anticipated expansion of this study to other academic centers.

### **7.3 Data Analysis Plans**

The primary data analysis plan is to compare the proportion of patients in each randomization arm experiencing a  $\geq 15$  point xerostomia score increase between baseline and 1 month, with the use of a two group chi-square test. As sample size allows, linear mixed effects models will be explored to evaluate changes over time including all repeated measurements. It is anticipated that a significant number of enrolled patients will be unable to complete the 3 month (estimated 40% response rate) and 6 month (estimated 20% response rate) post-radiation questionnaires due to disease morbidity and mortality, so modeling may be limited to the earlier time points. In such a

scenario with significant patient dropout, separate analyses will be performed for patients with vs. without long term follow up.

Descriptive statistics will be provided for all scores at all time-points and to summarize the patient population. Secondary data analyses will estimate the time to marginal relapse (defined as within 1 cm of the block edge overlying the blocked parotids) and the time to upper cervical spine relapse (defined as relapses in the C1 or C2 vertebrae) in each randomization arm using the Kaplan Meier method. A log rank test will be used to compare these time to event outcomes. Furthermore, the above analyses exploring xerostomia will also be conducted in all patients (including those who refused randomization but consented for the observational arm).

A linear regression model will be used to further explore the dosimetric relationship between parotid dose and xerostomia, to supplement data from LCCC 1540.

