## **1.0 BACKGROUND AND RATIONALE**

### **1.1 Study Synopsis**

The parotids have not been historically considered an organ at risk / avoidance structure and are not routinely delineated for whole brain radiation (WBRT) planning, despite receiving incidental dose [1] using standard fields. For this reason, we evaluated patient reported xerostomia in an ongoing prospective observational trial (LCCC 1540: Prospective Evaluation of Patient Reported Xerostomia After Whole Brain Radiation). At an interim analysis of LCCC 1540 with accrual at 90% of the goal, we found a clinically-meaningful rate of xerostomia following routine WBRT. Furthermore, the incidence/severity appeared to be related to parotid dose. The goal of this follow-up study is to investigate whether parotid sparing WBRT can reduce or prevent patient reported xerostomia. The study design will principally be a prospective randomized trial where patients are randomized to receive parotid sparing WBRT vs. standard WBRT where the parotids are not avoided. We will evaluate the xerostomia scores (using the University of Michigan Xerostomia Questionnaire [2]) of patients treated in each arm. Patients who refuse randomization will be offered enrollment in an observational arm to follow their symptoms of xerostomia for secondary analysis. This will be a multi-site study, with patients also enrolling at High Point Regional Health, High Point, North Carolina, as well as possibly other sites and institutions. We anticipate a total accrual of approximately 90 patients (45 in each interventional arm) with a goal of 62 evaluable patients reaching the primary 1 month post-RT endpoint.

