#### **4.3.2 Randomization Details**

Patients who agree to be randomized will be assigned to one of the following treatment groups using block randomization. A randomization list will be designed by the statistician. Patients will be randomized after informed consent is obtained, and before treatment begins. A list of randomized assignments will be provided to each site prior to enrollment of participants to facilitate ease of trial administration. This is done because of the often urgent nature of whole

brain cases and the necessity of clinicians knowing the randomized assignment before treatment planning.

Arm A: Standard WBRT (Control)

Arm B: Parotid sparing WBRT (Intervention)

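### Section 7.3 provides for separate longitudinal analyses by follow-up status, which is known only after randomization; any arm comparison within those parts loses the protection of randomization

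*Combined protocol and SAP*

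**What the plan says.** Section 7.3 (Data Analysis Plans) makes the 1-month comparison of proportions by chi-square test the primary analysis. It then adds a longitudinal analysis: "As sample size allows, linear mixed effects models will be explored to evaluate changes over time including all repeated measurements". It expects 40% of patients to answer at 3 months and 20% at 6 months, the rest being lost "due to disease morbidity and mortality, so modeling may be limited to the earlier time points". For that case it says "separate analyses will be performed for patients with vs. without long term follow up".

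Section 4.3.2 fixes the order of events: "Patients will be randomized after informed consent is obtained, and before treatment begins".

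Section 7.3 does not define long-term follow-up or significant dropout. It gives no rule for recombining the two parts, no sensitivity analysis for missing scores and no treatment of death. It does not say whether the separate analyses compare the arms or only describe the patients.

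**The concern.** Whether a patient is still answering at 3 or 6 months depends on survival, health and willingness, all observed after allocation. Randomization makes the arms comparable as a whole. It does not make them comparable among those who later respond, or among those who do not. If arm, or a symptom that arm affects, influences later response, the arms within each part differ for reasons other than treatment.

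Such a link is possible on the trial's own terms. The hypothesis is that arm changes xerostomia, and section 1.2.5 suggests that xerostomia may bear on quality of life and nutrition. Section 1.2 also says that the acute and early months matter most to these patients, and the mixed models are the only longitudinal score analysis that 7.3 names. The condition for splitting is met under the plan's own forecast, so this is the expected course and not a remote contingency.

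**Working it through.** The plan gives no figure for the split itself. The check takes its sample-size figures first, then precision, then possible bias.

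1. **Plan's own figures.** From 7.2: 42% v 14%, one-sided 0.05, 80% power. With pooled variance and mean proportion 0.28, n = [1.645·√(2·0.28·0.72) + 0.842·√(0.42·0.58 + 0.14·0.86)]² / 0.28² = 30.7, so 31 per group, as stated. 62/0.70 = 88.6, so 89 against the stated 90. Nothing below changes these.

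2. **Expected numbers.** With 90 randomized, 45 per arm (1.1): 1 month, 90 × 0.70 = 63 (31.5 per arm); 3 months, 90 × 0.40 = 36 (18 per arm); 6 months, 90 × 0.20 = 18 (9 per arm).

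3. **Precision.** The 95% half-width for an arm difference in mean change is t·26·√(2/n). The SD of 26 is the 1-month figure in 7.1, assumed to hold later.
   - n = 31.5: 2.000·26·√(2/31.5) = 13.1 points
   - n = 18: 2.032·26·√(2/18) = 17.6 points
   - n = 9: 2.120·26·√(2/9) = 26.0 points

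   The 3- and 6-month contrasts rest on about 36 and 18 responders whether or not the sample is split. The loss due to the split falls on the earlier time points. If long-term follow-up means a 3-month response, a 1-month contrast in the with part uses at most 36 of the 63 patients (17.6 points instead of 13.1). If all 36 also answered at 1 month, the without part has 63 − 36 = 27 patients: 2.060·26·√(2/13.5) = 20.6 points.

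4. **Bias if response depends on the score (assumed).** Take the 1-month change as normal with SD 26 and set the means so that 42% and 14% reach 15 points: 15 − 26·0.202 = 9.8 and 15 − 26·1.080 = −13.1, a difference of 22.8. Let the odds of later response be multiplied by 0.61 or 0.37 for each SD of higher score, with one intercept for both arms chosen to give the forecast overall response. The mean difference within each part is then:

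| Odds multiplier per SD | Overall response | With follow-up | Without follow-up |
|---|---|---|---|
| 0.61 | 40% | 21.6 | 21.7 |
| 0.61 | 20% | 21.9 | 22.0 |
| 0.37 | 40% | 18.9 | 19.3 |
| 0.37 | 20% | 19.4 | 20.4 |

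   The shrinkage runs from 22.8 − 22.0 = 0.8 to 22.8 − 18.9 = 3.9 points. The two parts differ by at most 1 point.

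5. **Bias if arm itself affects response (assumed).** A simulation had no true effect, frailty correlated 0.5 with the score, and an arm effect on response of 0.5 to 1.0 in log-odds. It gave spurious differences of 0.9 to 2.4 points in the with part and 0.6 to 2.0 in the without part. When response depended on frailty alone and not on arm, no bias appeared beyond simulation error.

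**The case against.** The strongest reply is that the sentence names no between-arm contrast, no test and no replacement of the mixed model. Looking at scores by dropout status is a standard way to see whether dropout is informative, and a descriptive reading is possible. This stands in part: a reader might infer that 7.3 commits to a formal arm test in each part, and the text does not say so. But 7.3 gives descriptive statistics a sentence of their own, whereas this one promises analyses and follows directly from the modelling. The wording leaves the arm comparison open.

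It is also true that the affected models are exploratory and run only if numbers permit. A reader might infer that the primary result is at risk. It is not: nothing in 7.3 splits the 1-month chi-square comparison, and neither secondary endpoint in 2.4 depends on the split.

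Third, a mixed model rests on missing at random, and examining dropout patterns is one way to probe that. This stands too. It is a reason for an analysis by pattern that returns one contrast for everyone randomized, not for two unconnected analyses.

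**Conclusion.** The point holds for the exploratory longitudinal analysis. Follow-up status is a post-randomization variable, so an arm comparison within each part lacks randomized comparability. It also discards information at the early time points: at most 36 of about 63 patients for a 1-month contrast among 3-month responders.

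The size of any bias is unknown. The documents give no data linking arm or xerostomia to later response; 7.3 attributes non-response to illness and death. The 1 to 4 points out of 22.8 rest on assumed odds multipliers and on a normal model that does not match the earlier study: it implies a mean change of +9.8 under standard treatment, while 7.1 reports +17.8, and a normal curve with mean 17.8 and SD 26 would put 54%, not 42%, at 15 points or more. The figures are illustrative, and small beside the half-widths.

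Two stronger readings are tempting. One is that the benefit would look very different in the two parts. On the responder scale the same assumed model turns a true 28 percentage points into about 12 to 22 in the with part and 29 to 30 in the without part. But the split in 7.3 follows a linear model of scores, and on that scale the parts nearly agree. The other is that the wide late intervals (17.6 and 26.0 points) are caused by the split. They come mostly from having few late responders, and removing the split would not create more questionnaires.

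**What to change.** In 7.3, replace the separate analyses with one linear mixed model containing arm, time and arm-by-time. It should use every observed score from every randomized patient, up to the last time point that can be fitted. Add a prespecified sensitivity analysis for dropout, for example a pattern-mixture model averaged over patterns to a single contrast for all randomized patients. Define long-term follow-up, and show scores by that status as description only, with no between-arm test.

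The cost is SAP wording and a little programming; sample size, conduct and the primary test stay as they are. Two limits remain. The mixed model assumes missing at random. The pattern-mixture check, which probes that assumption, will be imprecise with about 9 responders per arm at 6 months.

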#### **1.2.2 Whole Brain Radiation – Background and Quality of Life**

Whole brain radiation is commonly used for patients with multiple brain metastases. The prognosis of most patients who require whole brain radiation is poor, with many not living beyond six months [7]. Quality of life is thus of paramount importance in this population. Numerous prospective studies have reported on the well-known side effects of fatigue, alopecia, and neurocognitive decline following WBRT. This is balanced with the potential improvement in quality of life due to control of CNS disease [8-10]. While patients do occasionally complain of dry mouth following whole brain radiation, no prior studies have systematically assessed the frequency or severity of dry mouth in these patients, though one older case series did report several cases of parotitis following WBRT [11]. We believe that these symptoms are related to

incidental irradiation of the parotids, and that simple adjustments to the traditional RT fields can mitigate this toxicity.

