### **2.2 Secondary Objectives**

Secondary objective #1: To assess whether the use of parotid sparing WBRT fields results in an increase in marginal tumor relapses in the region of the blocked parotid glands *in randomized patients*.

Secondary objective #2: To assess whether the use of parotid sparing WBRT fields results in decreased xerostomia *in all patients, including randomized patients and patients who refused randomization but consented for the observational arm*.

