### **4.3 Study Details**

This is primarily a two-arm, single-blind, randomized study of parotid sparing WBRT, with a third observational arm of patients who were identified after radiation had already started or who refused randomization but were willing to be followed for quality of life assessment. The primary purpose of this study is to compare the proportion of patients experiencing significant xerostomia in patients randomized to parotid sparing vs. standard WBRT. Patients receiving WBRT often receive treatment in urgent situations, making pre-treatment randomization logistically challenging. Therefore, the observational arm serves to increase the number of eligible patients and allows for comparison of xerostomia in all patients receiving parotid sparing vs. standard WBRT, but who were unable to be approached in time for randomization. Patients enrolling on the randomization arms will be consented and enrolled prior to treatment. Patients enrolling on the observational arm may enroll up to 5 days after initiation of treatment. Post-treatment surveys will be collected up to 6 months post-RT. We therefore anticipate that patients' active participation will last approximately 6 months. Chart abstraction will take place for up to 1 year post-RT for assessment of secondary endpoint #1: freedom from marginal relapse.

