#### **4.3.11 Follow Up**

Follow up for the purposes of this study is limited to the administration of surveys up to six months post-radiation, which is the last planned questionnaire. Participation in this study will not impact the actual clinical follow-up schedule of patients receiving WBRT, which is based on the discretion of the treating radiation oncologist. Although a secondary endpoint is the rate of marginal relapse around the blocked parotid glands, this will be assessed using data obtained as part of standard of care follow-up of these patients. No additional visits or protocol-specified imaging will be required, as this would unnecessarily burden these palliatively treated patients, given the minimal expectation that a meaningful difference in tumor control exists (see section below on expected risks).

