3. For the same reason as above, omission of the C1/C2 vertebrae should also be of minimal significance. Given the overall poor prognosis of patients receiving WBRT, the rate of significant marginal bony relapses adjacent to the inferior WBRT field is expected to be extremely low. Furthermore, with the advent of stereotactic radiosurgery, any such relapses would still be safely treatable with definitive or palliative intent.
4. Finally, the willingness of many physicians and several institutions [1, 18-20] to adopt parotid sparing WBRT as their *current standard* is a testament to the generally low risk involved.

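### Secondary objective #1 asks whether parotid sparing increases marginal relapse, but its only formal comparison is a log-rank test that would probably miss a doubling or tripling; a confidence interval should give the answer

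*Combined protocol and SAP*

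**What the plan says.** Section 2.2 frames secondary objective #1 as a harm question in randomized patients: whether sparing "results in an increase in marginal tumor relapses in the region of the blocked parotid glands". Section 2.4 splits the endpoint into inferior-brain relapse near the block edge and relapse in C1 or C2. Section 7.3 estimates the time to each "in each randomization arm using the Kaplan Meier method" and then states: "A log rank test will be used to compare these time to event outcomes".

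The conditions under which that test will run are set elsewhere:

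- Section 1.1: 45 patients per randomized arm.
- Section 1.2.2: "The prognosis of most patients who require whole brain radiation is poor, with many not living beyond six months".
- Section 4.3: "Chart abstraction will take place for up to 1 year post-RT for assessment of secondary endpoint #1: freedom from marginal relapse".
- Section 4.3.11: "No additional visits or protocol-specified imaging will be required". Relapse is read from standard-of-care follow-up, whose timing the treating radiation oncologist decides.
- Section 4.4, on omitting C1/C2: "the rate of significant marginal bony relapses adjacent to the inferior WBRT field is expected to be extremely low". No rate is given for inferior-brain relapse.

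Section 7.2 sizes the trial for xerostomia only. For relapse, the documents give no expected events, power, sidedness, margin, interval for the between-arm difference, censoring rule or guidance on reading a non-significant result.

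**The concern.** A test of difference can answer a harm question only if it has a reasonable chance of detecting the harm. Here the protocol's own expectations (rare bony events, early death, a one-year window, imaging only when clinically ordered) point to a handful of events at most. Two endpoints tested separately thin them further. A non-significant p-value would then say almost nothing about whether sparing raises the risk.

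This matters because Section 1.3 makes safety part of the hypothesis under test, and gives the hypothetical risk of marginal failure as a reason some physicians keep standard fields. The relapse result therefore bears on whether sparing is adopted.

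Ascertainment adds to the problem. Only patients are blinded (Section 4.3.3), and clinicians know the assignment (Section 4.3.2). Imaging frequency could differ by arm in either direction, and the plan does not collect what would be needed to see it.

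**Working it through.** **The plan's own figure.** For xerostomia at 42% versus 14%, one-sided 0.05 and 80% power, the two-proportion formula with pooled variance and no continuity correction gives 31 per group (power 80.3%). At 70% completion, 62/0.70 = 88.6, so 89 against the stated 90. The sizing reproduces. There is no corresponding figure for relapse to reproduce.

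**Inputs for relapse.** From the documents: 45 per arm and a 12-month window. Assumed, because the documents give no value: one-year control relapse risk of 2%, 5% or, generously, 10% in a patient who survives the year; median survival of 4 or 6 months; hazard ratios (HR) of 2, 3 and 5; exponential times; every relapse before death found. The last assumption favours the plan.

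**Events needed.** Schoenfeld, 1:1 allocation, one-sided 5%, 80% power: E = 4(1.645 + 0.842)² / (ln HR)².
- HR 2: 24.7/0.480, so 52 events
- HR 3: 24.7/1.207, so 21 events
- HR 5: 24.7/2.590, so 10 events

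**Events expected.** Per arm: 45 × h/(h + d) × [1 − exp(−12(h + d))], where d = ln 2/median survival and h = −ln(1 − risk)/12, multiplied by the HR in the sparing arm. For the control arm at 2% and a 6-month median, h = 0.00168 and d = 0.1155, so 45 × 0.01437 × 0.755 = 0.49 events.

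**Power.** Log-rank simulation, 4,000 trials per row, one-sided critical value 1.645, death censored:

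| Control risk | Median survival (months) | Mean events, HR 2 | Power, HR 2 | Power, HR 3 | Power, HR 5 |
|---|---|---|---|---|---|
| 2% | 4 | 1.15 | 3.2% | 6.8% | 19.0% |
| 2% | 6 | 1.45 | 3.5% | 10.4% | 27.2% |
| 5% | 4 | 2.83 | 10.1% | 23.5% | 49.2% |
| 5% | 6 | 3.63 | 14.4% | 28.4% | 58.1% |
| 10% | 4 | 5.64 | 19.3% | 38.6% | 74.8% |
| 10% | 6 | 7.14 | 22.1% | 47.4% | 83.9% |

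The simulation standard error is at most √(0.25/4,000) = 0.8 percentage points. I therefore round the 2 to 5% range to 3 to 15% for HR 2 and 7 to 30% for HR 3. Two-sided testing at 5% lowers these to about 1 to 7% and 2 to 16%.

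**How few events can reject.** With equal numbers at risk and all E events in the sparing arm, the log-rank z is (E/2)/√(E/4) = √E. Three events give 1.73 and reject one-sided on the normal approximation. The exact one-sided p-value is 0.5^E: 0.125 for three events, 0.0625 for four and 0.031 for five. The simulation used the more lenient approximation.

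**What a reassuring result would leave open.**
- No events in 45 sparing patients, all fully followed: upper bound 1 − 0.05^(1/45) = 6.4%.
- Allowing for death, mean follow-up is [1 − exp(−12d)]/d = 5.0 to 6.5 months, or 18.9 to 24.3 person-years per arm. The zero-event bound is 2.996/24.3 = 0.12 to 2.996/18.9 = 0.16 relapses per person-year.
- Four events split evenly: the 95% upper limit for the HR is exp(1.96 × √(4/4)) = 7.1.

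**The case against.** The strongest defence is that this is a secondary endpoint in a small palliative trial sized for xerostomia. Low power for such an endpoint is normal, and Section 4.3.11 openly justifies requiring no imaging as a way to spare patients burden. Kaplan-Meier estimates by arm are also planned, so the log-rank test is not the only output. All of this stands. It means no larger trial and no added scans are called for. It does not supply an interval for the difference or a limit on what the test can be said to show.

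Several stronger readings are tempting, and the documents do not support them:

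- *The test cannot show an increase.* It can if the increase is very large: at HR 5, power is about 19 to 58% at 2 to 5% control risk and 75 to 84% at 10%.
- *All marginal relapse is expected to be extremely rare.* Section 4.4 says this of bony relapse only.
- *Patients never re-imaged will count as relapse-free until chart contact ends.* Section 7.3 states no censoring rule, so that treatment is possible but not documented. The supportable point is that the rule is missing.
- *The 40% and 20% response rates at 3 and 6 months show how few patients will be assessed for relapse.* Those are questionnaire rates; relapse comes from chart abstraction, and nothing links the two.
- *A null result will be reported as safety.* No section says so. What can be said is that nothing guards against that reading.

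**Conclusion.** The concern holds as a mismatch between question and method. Over the assumed 2 to 5% control risk and 4 to 6 month median survival, the chance of a non-significant one-sided result is about 85 to 97% if sparing doubles the hazard (100% minus 3 to 15%) and 70 to 93% if it triples it (100% minus 7 to 30%). Such a result would not support the safety part of the hypothesis in Section 1.3. Incomplete detection under discretionary imaging would lower power further.

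The relapse risks, hazard ratios and survival medians are my assumptions. At 10% control risk the test still has only 19 to 22% power for a doubling, so the conclusion does not depend on the lowest rates. The primary endpoint and the sample size are unaffected.

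**What to change.** In Sections 2.4 and 7.3:

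1. Make estimation, not the log-rank p-value, the answer to secondary objective #1. Report the number of events and the cumulative incidence by arm, with death as a competing event, separately for inferior-brain and C1/C2 relapse. Give the between-arm difference with a confidence interval from a named method that remains valid with few or no events, such as an exact or score interval. Usual Kaplan-Meier intervals degenerate when an arm has no events.
2. State that the upper limit of that interval is the safety conclusion, and that a non-significant log-rank test is not evidence of no increase. The log-rank test may stay as a supporting result.
3. State the censoring rule. In the chart abstraction already planned, record the date and region covered of each standard-of-care brain or cervical scan, and report imaging frequency by arm. Censoring at the last informative scan is suitable as a sensitivity analysis but not as the required rule: it gives never-scanned patients no time at risk, and clinically triggered scans can make the censoring informative.

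The cost is a few sentences of text, a per-scan record with a coverage judgement at each site, and a more modest safety statement. The scan fields should be added before abstraction closes.
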